	
1. Visit 1 (Day 1) - Screening/Baseline Visit: At Visit 1, study staff will explain the study procedures and an informed consent/assent must be signed prior to the initiation of any study-related procedures. At this visit, consenting/assenting subjects will have their medical history and demographics, concomitant medications and procedures/therapies, and inclusion/exclusion (I/E) criteria reviewed to determine subject eligibility. Subjects that require a “washout” period prior to enrollment into the treatment phase to meet I/E criteria requirements will be required to return to the clinic within 45 days to complete the remaining activities. Subjects who require “washout” for longer than 45 days will be re-consented. All WOCBP must have a negative UPT. A brief physical exam, vital signs (including height, and weight), clinical laboratory testing, photography, which is optional, at select site(s) per a photo guide provided by the Sponsor, and clinical evaluations will be performed prior to test article application. The Treatment Area will be defined as the entire body exclusive of a) the head and neck and b) mucosal areas*. The location of the IV to be treated and the percent BSA with IV in the Treatment Area will be recorded prior to test article application. Subjects who meet all inclusion criteria and no exclusion criteria will be randomized and assigned to the next available (lowest) subject number in ascending order. The test article will be weighed prior to dispensing to subjects. Test article, Subject Instruction Sheet, and Subject Diary with completion instructions will be dispensed. At this visit, study personnel will review the Subject Instruction Sheet and the subject and parent/guardian (if applicable) will be instructed on how and where to dispense and apply test article to all affected skin in the Treatment Area and to record applications in the Subject Diary. Subjects will apply the first dose of the assigned test article to all affected skin in the Treatment Area under staff supervision. Any adverse events (AEs) post-application will be recorded. Subjects will apply the assigned test article to all affected skin in the Treatment Area twice daily for up to 6 weeks. The subject will then be scheduled for Visit 2.
 
* Note disease on the neck and face if present may be treated with a bland moisturizer, but shall not be evaluated.
 
2. Visit 2 (Week 2, Day 15 ± 2) and Visit 3 (Week 4, Day 29 ± 2): Subjects enrolled into the study will return to the clinic at Weeks 2 and 4 for the study staff to perform the clinical evaluations, record percent BSA with IV in the Treatment Area, collect, review and dispense a new Subject Diary for test article compliance, update concomitant medications and procedures/therapies, record AEs, collect and weigh used test article and dispense test article if necessary. Photography, which is optional, will be performed at select site(s) per a photo guide provided by the Sponsor. Subjects whose IV is completely clear (IGA score = 0 and all clinical signs of IV = 0 [scaling = 0, fissuring = 0, and erythema = 0]) at Day 15 or Day 29 will complete the end of study (EOS) procedures. These subjects will have completed the study. Subjects whose IV is NOT completely clear will be instructed to continue twice daily treatment until the next visit and to record all applications in the Subject Diary. The subject will be scheduled for the next visit.
 
3. Visit 4 (Week 6, Day 43 ± 3 [OR Day 15 ± 2 or Day 29 ± 2 for subjects who are clear]) – End of Treatment/End of Study or Early Discontinuation: These activities may occur as scheduled at the end of the 43-day treatment period or earlier if (a) the subject is to be dropped from the study or (b) the subject’s IV within the Treatment Area is completely clear at Day 15 or Day 29. At this visit, the study staff will perform the clinical evaluations, record percent BSA

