--	---

	
with IV in the Treatment Area, perform clinical laboratory testing, perform photography, which is optional, at select site(s) per a photo guide provided by the Sponsor, update concomitant medications and procedures/therapies, record AEs, collect and review the Subject Diary for test article compliance and collect and weigh used test article. A UPT will be performed on all WOCBP. All subjects will exit the study.

Study Measurements	
At each visit, the skin affected with IV in the Treatment Area defined at the Baseline Visit will be assessed as follows:
 
Efficacy: Investigator’s Global Assessment The IGA score is a static evaluation of the overall or “average” degree of severity of a subject’s disease, taking into account all of the subject’s scaling, erythema, and fissuring in the Treatment Area by the investigator or designee as the subject appears on the day of the evaluation. This evaluation takes into consideration the three individual characteristics of IV (scaling, fissuring, and erythema) as well as hyperpigmentation with the IGA score at each visit representing the average degree of scaling, fissuring, and erythema (<math>\pm</math> hyperpigmentation, if present) that is eligible for treatment. IGA will be assessed using the following 5-point scale: clear (0), almost clear (1), mild (2), moderate (3), or severe (4).
 
Clinical Signs of Ichthyosis Vulgaris Scaling, fissuring, and erythema in the Treatment Area will be graded using the following 5-point scale: clear (0), almost clear (1), mild (2), moderate (3), or severe (4).
 
The degree of hyperpigmentation relative to the subject’s normal skin color associated with the disease affected skin in the Treatment Area will be graded using the following 5-point scale: none (0), minimal (1), mild (2), moderate (3), or severe (4).
 
[REDACTED]
 
[REDACTED]
 
[REDACTED]
 
[REDACTED]
 
[REDACTED]

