	
Pruritus At the Baseline Visit, prior to the first application of the test article, the subject's overall experience of pruritus within the previous two weeks will be assessed using a questionnaire (5-D Pruritus Scale). At all follow-up visits, the overall experience of pruritus, in the previous two weeks, will be scored using the same questionnaire. Pruritus assessed by this evaluation should be reported as an AE only if therapy is required.
 
Percent Body Surface Area with Active Ichthyosis Vulgaris in the Treatment Area The percent BSA with active IV within the designated Treatment Area will be calculated at Baseline and at all follow-up visits.
 
Safety: Test Article Compliance Subjects will apply the first dose of test article to skin affected with IV within the Treatment Area under staff supervision. Subjects will be instructed to record the date and time that each dose was applied. At each visit, subject diaries will be reviewed and subjects will be counseled regarding compliance, if necessary. All dispensed test article will be weighed at each visit and will be recorded.
 
Adverse Events All AEs will be recorded. At each visit after the Baseline Visit/Day 1, subjects will also be questioned specifically about the status of any ongoing AEs.
 
Clinical Laboratory Testing and Pregnancy Testing Chemistries, hematology, and urinalysis and UPTs will be performed at Baseline and EOS.

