
 Subjects with Baseline scores of 0 or 1 will be excluded from summaries and analyses of success rates unless the corresponding sign score at follow-up visits is >1.

	
Safety Analyses:
 
Dosing Compliance Descriptive statistics will be used to summarize test article compliance for the ITT population. Measures of test article compliance will include the duration of treatment (number of days dosed), the total number of applications (determined from the actual number of applications reported by the subject), and the percent of expected doses applied. A subject will be considered compliant with the dosing regimen if the subject applies at least 80% but no more than 120% of the expected number of applications.
 
Extent of Exposure The total amount of test article used (grams of test article applied) will be calculated from the weights of the returned test articles. Descriptive statistics (mean, median, SD, minimum and maximum) will be determined for the total amount of test article used by each subject by treatment group.
 
Clinical Laboratory Testing, and Urine Pregnancy Testing A listing of the clinical laboratory results and UPT results will also be prepared.
 
Adverse Events All AEs reported during the study will be listed, documenting onset, whether therapy was required, any change in test article dosing, severity, possible relationship to test article, and outcome. Verbatim terms on the case report forms (CRFs) will be linked to preferred terms (PTs) and system organ class (SOC) using the Medical Dictionary for Regulatory Activities (MedDRA) mapping system. All reported AEs will be summarized by the number of subjects reporting AEs, SOC, PT, severity, and relationship to test article by treatment group.

--	--

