## SCHEDULE OF EVENTS

Study Day	Visit 1 Screening/ Baseline  Day 1	Visit 2 Week 2 Day 15 (±2)	Visit 3 Week 4 Day 29 (±2)	Visit 4 Week 6 EOT/EOS Day 43 (±3) 
Informed Consent/Assent	X			
Inclusion/Exclusion Criteria	X 			
Urine Pregnancy Testing  for WOCBP 	X 			X 
Medical History/Demographics	X			
Brief Physical Exam	X			
Vital Signs, Height, & Weight	X			
Clinical Evaluations (IGA, Clinical Signs of IV, ██████, Pruritus)	X  (prior to test article application)	X	X	X
Record percent BSA with IV in the Treatment Area	X	X	X	X
Randomization to Treatment Regimen (Subject # Assignment)	X			
Provide (or review) Instruction Sheet to Subject & Parent/Guardian (if applicable) and Demonstrate How to Apply the Test Article 	X	X	X	
Provide Subject Diary to Subject & Parent/Guardian (if applicable) and Completion Instructions	X			
Clinical Laboratory Assessments	X 			X 
Photography (Select Sites)	X	X	X	X
Review/Dispense/ Collect Subject Diary		X	X	X
Weigh/Dispense Test Articles	X	X	X	
Weigh/Collect Test Articles		X	X	X
Instruct Subject to Continue Twice Daily Treatment	X	X	X	
Record Concomitant Medications and Procedures/Therapies	X	X	X	X
Record Adverse Events	X	X	X	X 

1. Screening assessment may be performed up to 45 days prior to the Baseline Visit for those qualified subjects that are eligible to enroll in the study but require wash-out of medications prior to enrolling into the treatment phase of the study. Screening and Baseline activities may be combined into a single visit if the subject does not require washout.
2. This activity may occur at an earlier visit if the subject is discontinued from the study.
3. For those subjects that required a washout period related to exclusionary medications, need to reaffirm these subjects meet all protocol requirements at the Baseline Visit.
4. UPTs must have a minimum sensitivity of 25 mIU β-hCG/mL of urine.
5. WOCBP include any female who has experienced menarche or is 10 years of age or older and who has not undergone successful surgical sterilization (hysterectomy, bilateral tubal ligation (within six months of initiation of treatment), or bilateral oophorectomy) or is not postmenopausal (defined as amenorrhea >12 consecutive months in women 50 years of age and older).
6. See application guidelines per protocol and in the subject instruction sheet.

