7. Perform laboratory tests (blood chemistries, hematology, and urinalysis).
8. Any treatment related AEs that are ongoing at EOS must be followed until resolution or stabilization.

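### Footnote 8 of the Schedule of Events requires follow-up after end of study only for treatment-related AEs, so an SAE judged unrelated and still ongoing at exit has no required follow-up in the supplied text

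*Combined protocol and SAP*

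**What the plan says.** The follow-up rule is footnote 8 of the Schedule of Events, attached to the Visit 4 cell of the row for recording adverse events: "Any treatment related AEs that are ongoing at EOS must be followed until resolution or stabilization".

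While the subject is on study, AE status is checked whatever the cause. The Protocol Synopsis (Study Measurements, Safety, Adverse Events) states: "At each visit after the Baseline Visit/Day 1, subjects will also be questioned specifically about the status of any ongoing AEs".

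Exit takes place at Visit 4, which also serves as the early discontinuation visit. The synopsis closes its description of that visit with "All subjects will exit the study". It can be held "earlier if (a) the subject is to be dropped from the study", and schedule footnote 2 says the same of discontinued subjects: "This activity may occur at an earlier visit if the subject is discontinued from the study". Subjects who are completely clear at Day 15 or Day 29 also have their EOS procedures then: "These subjects will have completed the study".

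For reporting, the synopsis (Statistical Methods, Safety Analyses, Adverse Events) lists every AE reported during the study. The listed fields end with "severity, possible relationship to test article, and outcome". The summaries are specified separately: "All reported AEs will be summarized by the number of subjects reporting AEs, SOC, PT, severity, and relationship to test article by treatment group".

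SAEs appear once as a category, within the safety endpoints (Study Endpoints). Nothing there says how long an SAE is followed.

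**The concern.** AE questioning during the study and the AE listing both ignore causality. After exit, required follow-up depends on it entirely. The event most in need of a known outcome is a serious one, and seriousness plays no part in the rule.

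The decision whether to follow an SAE then rests on the causality judgement available at exit, and no later visit is scheduled at which that judgement would be looked at again. If the event is called unrelated and the subject leaves, the supplied text obliges nobody to find out how it ended. The study enrols subjects from 12 years of age, so some of those affected could be minors.

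The stake is mainly subject safety. Secondarily, the outcome field for such an event may read only as ongoing.

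**Working it through.** No statistical calculation applies and the plan gives no figure to reproduce. The check is whether any text in the synopsis or schedule creates a duty to follow an AE after exit, and which events that duty reaches.

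**Step 1. Candidate provisions, and whether each extends beyond exit**

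| Provision | Location | Depends on causality? | Applies after exit? |
|---|---|---|---|
| AEs recorded at each visit | Schedule of Events | No | No; the last column is Visit 4 |
| Status of ongoing AEs asked at visits | Synopsis, Study Measurements, Safety | No | No; tied to visits |
| SAEs named as a safety endpoint | Synopsis, Study Endpoints | No | No; no follow-up duty stated |
| Outcome listed for each AE | Synopsis, Safety Analyses | No | No; a listing, not a duty to obtain data |
| Follow-up of ongoing AEs | Schedule, footnote 8 | Yes | Yes |

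One provision reaches past exit, and it is the one limited by causality.

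**Step 2. Contacts after EOS.** The synopsis gives treatment duration as up to 6 weeks and individual study duration as up to 6 weeks. The two are equal, and all subjects exit at Visit 4. Scheduled contacts after EOS: 0.

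**Step 3. Events ongoing at exit, by type**

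| | Judged related | Judged unrelated |
|---|---|---|
| Non-serious | Follow-up required | Not required |
| Serious | Follow-up required | Not required |

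A treatment-related event is covered whether or not it is serious. It is also covered when it leads to withdrawal, because footnote 8 sits on the visit that doubles as early discontinuation. The cell of concern is the lower right. The upper right is a reasonable place to stop in a short topical study.

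**Step 4. Does the route of exit matter?** A subject may leave at Week 6, on being dropped, or on complete clearance at Day 15 or Day 29. The rule is the same in each case, so the gap is too. Early exit changes when questioning stops; it does not measure what the rule omits. A subject who stops the cream but remains in the study is still questioned at the remaining visits and is outside this point.

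**Step 5. Effect on reported results.** The listing has 6 named fields: onset, therapy required, change in dosing, severity, relationship and outcome. The summaries use the number of subjects, SOC, PT, severity and relationship. Outcome is 1 of 6 listing fields and enters 0 of the summaries. A missing later outcome therefore changes no AE count, no planned AE table and no efficacy analysis.

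**The case against.** The strongest reply is that this is an abridged text. It runs from the synopsis to the schedule footnotes and contains no AE or SAE section: no SAE definition, reporting timeline or causality scale. The schedule itself refers the reader to the protocol for application guidelines, so fuller text exists. SAE follow-up is something one would expect in the missing section, and silence here says little about what that section contains. This stands. A reader might infer that the trial has no SAE follow-up rule; the documents cannot support that. What survives is that footnote 8 is a stated rule, not silence. It draws its line at causality, and a site working from the schedule would see only that line.

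It can also be said that footnote 8 is a minimum. That stands too: it closes no event and forbids no further follow-up, so it would be wrong to read it as barring follow-up of unrelated events.

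A third reply is that limiting mandatory follow-up to related events is a legitimate choice in a Phase 2 topical study of up to 6 weeks. For non-serious events this is fair. A reader might want the rule to cover every AE leading to withdrawal, but nothing in the documents shows that a non-serious, unrelated event in someone who has left needs open-ended follow-up. That is a debatable trade-off and no part of this point.

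Finally, the listing does not promise a final outcome, and an entry of ongoing would satisfy it. This is correct, so the argument does not rest on a breach of the listing plan.

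**Conclusion.** The point holds within the supplied synopsis and schedule: an SAE judged unrelated and ongoing at exit has no required follow-up there. It is a cheap improvement to subject protection, not a flaw in the analysis.

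The number of affected events cannot be derived from the documents. With approximately 88 subjects treated for up to 6 weeks it is likely very small and may be zero; that is a judgement, since no SAE rate is given. A reader might infer that AE rates would be understated or the comparison of arms distorted. Neither follows, because an event already recorded stays in the AE listing and summaries whatever its later outcome.

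The conclusion rests on two assumptions: that footnote 8 means what it says in restricting the duty to treatment-related events, and that no SAE rule in the unseen protocol text already widens it. If the second fails, what remains is a footnote narrower than the protocol it summarises, which is still worth aligning.

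**What to change.** Change the scope of footnote 8 so that its subject becomes *all treatment-related AEs, and all SAEs regardless of judged relationship*. Leave the rest of the footnote as it is: the trigger (ongoing at EOS) and the stopping point (resolution or stabilization).

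Before issuing it, the sponsor should check the safety section of the full protocol. If an SAE follow-up rule is already there, word footnote 8 to match it, so that the schedule and the protocol body do not give sites two different duties.

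The change adds no scheduled visit, procedure or analysis. The downside is a few extra contacts after exit for any subject with such an event. These could be prolonged if the event is slow to settle, and may involve a subject who chose to leave.
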